11. RECRUITMENT AND PROCEDURES PREPARATORY TO RESEARCH

Subjects will be recruited from the following sources: 1) IRB- approved flyers or advertisements, with prospective subjects initiating contact with the research staff, 2) Persons who have participated in prior research studies from our laboratory or affiliated laboratories who have indicated that they would like to be contacted to hear about potential research studies, 3) Patients from the UCSD Pulmonary and Sleep Center, UCSD Owen Clinic, and VA SPID clinic who have indicated that they are interested in hearing about research opportunities, and 4) Persons who have been identified via SlicerDicer

Identifying Eligible Subjects with Partial HIPAA Waiver

A temporary waiver of consent and partial waiver of HIPAA authorization is requested for this study in order to: 1) Pre-screen persons (from sources 2 and 3 above) who meet the inclusion and exclusion criteria, and 2) Perform telephone or in person interviews with potential subjects for screening of inclusion and exclusion criteria prior to obtaining consent. The following points justify the waiver of consent: 1) Private information that will be reviewed is non-sensitive, and anyone pre-screened will have previously agreed to contact for research, 2) No research procedures will be performed without consent, so there should be minimal possibility of adverse effect on potential subjects, 3) Adequate enrollment could not be achieved without accessing this information, since specific medical conditions are being investigated, 4) All persons contacted will be provided with information about our screening procedures. For the partial HIPAA authorization: 1) Any PHI accessed for screening will be kept by research staff until either consent is obtained, or it will be destroyed immediately if consent and HIPAA authorization is not obtained, 2) Identifying potential subjects and then contacting/approaching them to discuss the research will require accessing PHI, 3) Minimal necessary PHI will be accessed and kept only temporarily while that subject is being screened, as above, 4) PHI will only be accessed by members of the research team included in the IRB, and will include name, date of birth, medical record number, contact information, and diagnoses.

SlicerDicer

Slicer Dicer will be used to identify both Summary & Patient Level Requests:

Researchers plan to use UC San Diego Health's Epic SlicerDicer, a self-service cohort discovery tool.

Researchers will have access to direct summary and patient level data. Using SlicerDicer, researchers will: Review the charts at a patient level to identify potential patients for recruitment.

We will be identifying patients with Human Immunodeficiency Virus (HIV), ages 18-65 years, and without other known untreated sleep fragmenting disorder. We will create a call list with the patient's name, phone number, and email address. This call list will be stored digitally under password protection on a UCSD secured drive shared between the research team. Once identified, an investigator of the study team will contact the patient to ask if they are interested in hearing about sleep medicine research study opportunities. If yes, the study team member will provide full details about the study. If no, the patient's name will be removed from the call list. All Epic Slicer Dicer users will have access and security provided by UCSD's Epic access team.

Prospective subjects will also be recruited from the community after individuals have initiated contact with the research staff. Permission to distribute IRB approved messages and flyers is being requested for the following

sites and locations.

UCSD Listserve, UCSD Hospital Bulletin Board, Facebook, Craigslist, UCSD CTRI REDCap Survey
IRB approved flyers will be digitally posted on the UCSD Listserv, Facebook, and Craigslist. The flyers will also be placed on UCSD Hospital Bulletin Boards by the Community Engagement Manager for the Clinical Transitional Research Institute (CTRI).

Facebook Page Welcome Message

We are requesting permission to have this message posted on a Facebook page created for recruitment purposes.

Welcome to the UCSD Pulmonary and Sleep Medicine Research group's Facebook page. We have ongoing research studies, primarily investigating obstructive sleep apnea. If you or someone you know has obstructive sleep apnea, please see our IRB approved flyers below. Occasionally, we are looking for healthy individuals without sleep disorders. Please regularly check our page for flyers describing these research opportunities.

Research Match

ResearchMatch will be used to contact prospective subjects with an IRB approved recruitment message. The message will be submitted for approval in an amendment if it is not already included with the initial project submission.

Department of Motor Vehicles Booth

The Research Team will set up a booth between the hours of 8AM-5PM outside of the Clairemont Department of Motor Vehicles (DMV) at [name] to distribute IRB approved flyers. A permit application for Activity on State Property will be submitted to the California Highway Patrol for approval at least 30 days before the booth is prepared.

Radio Station (list of radio stations)

We are requesting permission to have the following message broadcasted on iHeartMedia San Diego radio stations--Star 94.1, 101.5 KGB, Channel 93.3, Rock 105.3, XTRA 1360 Fox Sports, KOGO: 600 AM, JAM'N 95.7--KPBS 89.5 FM, Jazz 88.3 FM, KFSD 1450 AM, KURS 1040 AM, and AM 1170 The Answer:

UCSD Pulmonary and Sleep Medicine Research is offering research study opportunities, primarily for people with sleep apnea. If you or someone you know suffers from obstructive sleep apnea, contact us at [contact] or [contact] for more information.

When this message is IRB approved, it will be submitted only to the radio stations listed above. We will request permission for any additional radio broadcasting stations.

Research Group Website

The UCSD Pulmonary and Sleep Medicine Research group has a webpage hosted by UCSD health sciences. Wording from IRB approved flyers will be posted there.

UCSD CTRI REDCap Survey

Prospective subjects can voluntarily choose to fill out a UCSD CTRI REDCap Survey for this protocol. Information will be securely collected and stored via REDCap and will be used to determine if the prospective subject is eligible for the study.

MyChart Messages

UCSD Owen clinic patients may be sent a letter via MyChart by their clinicians inviting them to participate in this research study. Please see the document entitled "MyChart Letter for Owen Clinic patients" for the message.

12. INFORMED CONSENT

The research coordinator will screen the subjects over the telephone (or in person for clinic patients, time and patient preference allowing) following the screening script. A waiver of documented consent will be requested and once oral consent by the subject is obtained this consent will be used for the sole purpose of discussing the study with the subjects over the phone and performing the screening process as needed. The reason for this is because the only record linking the subject and the research would be the consent document and the principal risk would be potential harm resulting from a breach of confidentiality. Individuals interested in participating in this study will be given detailed explanation of the procedures, potential benefits, risks and discomforts of the study by the study researchers listed in the IRB application. All study staff are CITI certified and the importance of following GCP and HIPAA rules has been impressed upon them by the PI. Staff obtaining consent will have sufficient knowledge of the study to answer any questions that might arise during the consent process.

A copy of the consent form will be given to the potential subject by email a minimum of 48 hours in advance of any planned baseline visit. If the individual agrees to participate, they will meet with research staff in person prior to any data collection to obtain written informed consent. Subjects who have given a written consent will be given a copy of the signed consent form. The original consent and HIPAA authorization will be kept in the subject's research file in a locked cabinet. No research procedures will be performed prior to obtaining informed consent.

English will be used in all discussions during the consent process. The patient will be excluded from the study if their preferred language is one other than English or if they do not understand English. The information being communicated will not include any exculpatory language through which the potential subject will waive or appear to waive any of the participant's legal rights or release or appear to release the Researcher, Sponsor, the University or its agents from liability for negligence. Subjects unable to give their own consent will not be included in the study.

As this study is separate from any clinical care, a waiver of the requirement to upload the consent and HIPAA waiver into the electronic medical record is requested.

13. ALTERNATIVES TO STUDY PARTICIPATION

The alternative to study participation is not to participate. Subject may choose not to participate in this research study if they wish.

14. POTENTIAL RISKS

Sleep Studies: During the sleep portion of the study, there may be discomfort at the electrodes sites; a localized skin irritation/allergy can occur due to application of the skin surface electrodes for EEG, EKG, and EMG recordings. Subjects may be sleepy after participating in our physiology studies if they have poor sleep.

During the physiological sleep studies, the tight-fitting nasal mask could lead to skin irritation, nasal congestion, and/or nasal dryness. Short periods of apnea during the study would not be expected to cause side effects, other than the possibility of awakening from sleep. Finally, when using positive pressure or having one's mouth taped closed, there is a rare risk of vomiting, which could in turn lead to aspiration, but this is

exceedingly rare and minimal overall risk.

For esophageal catheter placement, there is mild discomfort associated with passing the catheter through the nose and potential gagging or even vomiting as the catheter passes through the pharynx. However, once in place the catheter is not uncomfortable and is well tolerated. All subjects will have fasted for at least four hours prior to the study and thus their stomach content is minimal. The mask can be easily removed if needed for any reason. For these reasons we believe there is a minimal risk of aspiration or other complication from this portion of the study.

Venipuncture: Local bruising and soreness can occur, which are usually mild and self limited.

EndoPAT: Tingling of the hands following cuff inflation can cause discomfort but goes away within a few minutes. No permanent injury has been reported by the manufacturer.

Lung function testing: The test is routinely performed in clinical practice with few associated risks. Lightheadedness or coughing may be induced by forceful breathing.

Loss of Confidentiality: There is a risk of loss of subject confidentiality. We will protect all subject information to the best of our ability so this will not happen, as detailed in subsequent sections.

15. RISK MANAGEMENT PROCEDURES AND ADEQUACY OF RESOURCES

We believe the risks of our research are quite minimal. All recordings will be performed in the closely monitored environment of our research laboratory in the CTF, CTRI, or MTF. Emergency equipment and personnel are readily available in the unlikely event of a serious complication.

Following the overnight study, subjects will have the option of sleeping, without instrumentation, for as long as they would like before driving home. We will offer them a cab voucher to have a cab take them home. They will only drive home if they feel adequately rested to do so and is corroborated by an assessment by a health professional (MD, PhD, or equivalent) trained in sleep medicine. The subject will be assessed for excessive sleepiness. If subject does not feel comfortable driving home, we will offer them a cab or they will be allowed to continue sleeping.

Subjects will be given a phone number to report any post-study complications, which will be personally reviewed by the PI to determine whether they require additional follow up or warrant reporting to the IRB as a serious unanticipated event. Because this is a research study, there may be some unknown risks that are currently unforeseeable. Any abnormal findings discovered as part of the study, will be relayed to the subject and, if requested, to their PCP. For example, persistently high blood pressure measurements or high fasting glucose will be communicated to the subjects and to their doctor.

DSM Report

A data safety monitoring report will be prepared at least annually and included with reports to the UCSD HRPP (yearly continuing review) and the funding agency (yearly progress report). In addition to enrollment, it will track:

- 1) All adverse events in which abnormal testing results were conveyed to the subject.
- 2) All adverse events in which abnormal testing results were conveyed to a subject's designated physician. (A record of this communication will be kept in the patient's file.)
- 3) Any other adverse events, serious adverse events, and unanticipated problems, all of which will be adjudicated and classified as study-related or unrelated to the study.
- 4) The report will also include amendments to the study protocol.

This yearly report will be comprehensive; however, more prompt reporting may be needed.

16. PRIVACY AND CONFIDENTIALITY CONSIDERATIONS INCLUDING DATA ACCESS AND MANAGEMENT

There is always the risk of subject information being released accidentally. We will make every effort to maintain patient privacy and confidentiality both during and following the study. Electronic study data will be de-identified by substitution of codes for names and hospital identifiers and will be stored on a secure disk for access by Investigator and study staff only and any hard copies will be stored in a locked cabinet. In all correspondence and in internal study reports that require identification of individual subjects, subjects will be referred to and known by their ID number and character name code. HNRP staff will have access to data collected from research subjects that have previously participated in protocol with their research division. All subject data forms (CRF's) will only list the ID number. All research staff are CITI certified and have had impressed upon them the importance of confidentiality. This study does not involve the collection of sensitive personal information from subjects. Data will be stored only at UCSD sites and its use will be confined to that specified in this protocol and its approved amendments.

Data generated as a result of this study will only be made available for inspection upon request of the UCSD Human Research Protection Program or the study sponsor.

17. POTENTIAL BENEFITS

Subjects who participate may derive benefit if a previously unknown sleep disorder such as obstructive sleep apnea is diagnosed and treated. Subjects who are not found to have OSA or other sleep disorder are unlikely to derive benefit. Society in general may benefit as this study will help achieve a more complete understanding of breathing disorders.

18. RISK/BENEFIT RATIO

The investigators feel risks associated with these studies are outweighed by the benefits.

19. EXPENSE TO PARTICIPANT

There will be no cost to the subject for participating in this study. All of the tests and procedures that will be done for this research will be paid for by study funds. We will pay for any sleep studies done for research purposes.

Subjects diagnosed with sleep apnea who are recommended to undergo treatment for OSA and elect to do so may have expenses incurred. For example, they may have a co-pay as part of their clinical sleep evaluation, or as part of their OSA treatment.

20. COMPENSATION FOR PARTICIPATION

Subjects will be compensated after completing each portion of the study, as outlined below:

- Daytime Visit 1 (Aim 1): \$50
- Overnight Visit 1 (Aim 1): Routine Polysomnography: \$100
- Actiwatch returned (Aim 1): \$50
- Overnight Visit 2 (Aim 2): Research Polysomnogram: \$100
- Weekly Phone calls (Aim 3): Subject will be compensated for \$20 for answering each weekly follow-up call for 12 weeks, in total of \$240.
- Daytime Visit 2 (Aim 3): Day Testing \$50
- Actiwatch Returned (Aim #3): \$50
- If a separate visit needs to be scheduled for the fasting morning blood sample: \$20 for each visit
- If an additional daytime visit is needed for data collection: \$50
- If data is inconclusive and an additional polysomnogram night is required, they will be paid \$100.

Subjects will make up to a total of \$-660.00 for completion of the all study aims, unless additional data needs to be collected.

If subjects only complete Aim 1, compensation will be \$200.00.

If subjects only complete Aim 1 and Aim 2, compensation will be \$300.00.

Parking will be available free of charge and participants will also be reimbursed for minor out of pocket expenses including meal vouchers, public transportation or taxi vouchers. If the subject terminates the study early, they will receive an amount based on the visits that have been completed. If any of the visits are missed, the subject will not be compensated for those visits.

23. FUNDING SUPPORT FOR THIS STUDY

Funding from NIH under 1R01HL142114-01

24. BIOLOGICAL MATERIALS TRANSFER AGREEMENT

Not applicable

25. INVESTIGATIONAL DRUG FACT SHEET AND IND/IDE HOLDER

Not applicable

26. IMPACT ON STAFF

This study is outside of any clinical care and thus will not impact any staff outside the research personnel. It is anticipated that we will diagnose 60 subjects with sleep disorders that require clinical evaluation over 4 years. This volume of patients can easily be handled by the UCSD Sleep Medicine clinic.

27. CONFLICT OF INTEREST

The PI and any key personnel associated with this study do not have any financial interests or other conflicts related to this study.

28. SUPPLEMENTAL INSTRUCTIONS FOR CANCER-RELATED STUDIES

This study will include enrollment of cancer patients. PRMC has determined that this protocol is not cancer-related.

29. OTHER APPROVALS/REGULATED MATERIALS

Not applicable

30. PROCEDURES FOR SURROGATE CONSENT AND/OR DECISIONAL CAPACITY ASSESSMENT

Not applicable

Obstructive Sleep Apnea Endotypes and Impact on Phenotypes of People Living With
HIV

Statistical Analysis Plan

NCT03575143

October 5, 2018

Statistical Considerations:

Results will be reported as point estimates (odds ratios or mean differences across groups, as appropriate) and interval estimates (95% confidence intervals). All tests of significance for the secondary outcomes will be 2-sided and Bonferroni adjustments will be made for multiple comparisons as appropriate. A p-value of 0.05 will be considered statistically significant. Statistical analysis will be conducted using the statistical software R 3.3.3. (www.rproject.org). Demographic and baseline characteristics will be compared among the cases and controls using Fisher's exact test for categorical variables, and a two-sample t-test for continuous variables. Appropriate non-parametric alternatives will be considered, if parametric assumptions fail.

Aim 1 – Sleep and Activity Phenotyping

To compare the symptoms of PLWH+OSA vs. PLWH–OSA. This aim will allow us to test the hypothesis that fatigue is overexpressed in PLWH+OSA compared to PLWH–OSA, independent of known covariates.

Sample Size Justification: The study is expected to enroll 120 evaluable HIV subjects, not known to have OSA, or not on treatment for OSA, and not known to have any other sleep disorder (such as narcolepsy) other than symptoms of insomnia. Based on the literature cited above, we expect to find a 50% prevalence of OSA (defined as an AHI >5/hour using 4% criteria) such that 60 subjects will have OSA and 60 will not. FACIT-F scores in HIV have been reported by two groups with remarkably similar means and standard deviations (Ref 64, 108). The presence of witnessed apneas was associated with a 6.5 reduction in FACIT score (with 3 points considered clinically meaningful, lower scores are associated with worse fatigue). Therefore, assuming a mean FACIT-F score of 36 in those without OSA and 30 in those with OSA, and a standard deviation of 12 in both groups, we will have approximately 80% statistical power to detect a difference between the two groups. Power is based on a two-sided, two-sample t-test, assuming alpha is set to 0.05. To account for 10% attrition, we will enroll 134 subjects to achieve 120 evaluable subjects.

Statistical Analysis Plan: First, we will evaluate if there is a difference in the primary outcome, FACIT-F scores, between OSA and non-OSA participants using a two-sample t-test. Multiple regression modeling will be used to assess the association between FACIT-F scores and OSA status (dichotomous independent variable), adjusting for other potential covariates, such as age, OSA severity (AHI), medications, mean sleep duration as assessed by actigraphy, and inflammation as assessed by CRP or similar such as IL-6.

Aim 2 – OSA Endotyping

Data Analysis: From the research PSG, the upper airway collapsibility as defined by the critical closing pressure (Pcrit) will be analyzed according to published methods. Additionally, the relevant traits will be extracted with the aid of MATLAB (Natick, MA) and our custom software. The traits will then be plotted on the axes ventilation vs. ventilatory demand to produce an individual assessment of the relevant traits for each subject

Aim 2: In those PLWH found to have OSA, we will perform detailed physiological assessments to determine endotype. This aim will allow us to test the following hypotheses:

Hypothesis 2A: To compare neurocognitive performance (PVT) in PLWH+OSA with a low arousal threshold (wake up too easily) vs. those with a high arousal threshold. This aim will allow us to test mechanistically the hypothesis that stratified for similar disease

severity, low arousal threshold induced OSA yields worse neurocognitive dysfunction compared to equal severity OSA with high arousal threshold.

Hypothesis 2B: To compare endothelial dysfunction via arterial tonometry in PLWH and OSA with a high loop gain (ventilatory instability with associated hypoxemia/hypercapnia) vs. those with low LG. This aim will allow us to test the hypothesis that stratified for similar disease severity, LG-induced OSA yields worse endothelial function compared to equal severity OSA with low LG.

Sample Size Justification: Of the 120 PLWH studied in Aim 1, we believe that at least 60 will have OSA. We will split the cohort of those with OSA into high and low arousal threshold at the median value for the group. Although we will have multiple markers of cognitive function, our main outcome for Aim 2A for statistical purposes will be the psychomotor vigilance test (PVT). Prior work by Kribbs and colleagues reported a mean reciprocal reaction time of 3.9 seconds⁻¹ with a standard deviation of 0.5 (Ref 112). We believe that a change of 0.3 seconds⁻¹ represents a clinically important difference based on the effect size of CPAP observed with prior studies (Ref 123). Therefore, assuming a mean reciprocal reaction time of 3.9 seconds⁻¹ in those with low arousal threshold OSA and 4.2 seconds⁻¹ in those with high arousal threshold OSA, and a SD of 0.5 in both groups, we will have adequate power (beta >0.8) to detect a difference between the two groups (alpha = 0.05).

Statistical Analysis Plan: We will evaluate if there is a difference in PVT in OSA participants with low vs high AT using a two-sample t-test. As a sensitivity analysis, we will consider multiple regression models adjusting for additional covariates such as age, AHI, medications, mean sleep duration via actigraphy, and inflammation as assessed by CRP or IL-6 may be included in the modeling if significantly associated with outcome (p<0.10).

Aim 3 – Impact of OSA treatment on Sleep and Activity Phenotypes

To test in PLWH+OSA whether 3 months of PAP treatment results in changes in OSA manifestations. This aim will allow us to test the hypothesis that endotype underlying OSA will be predictive of the specific clinical improvements seen in adherent users of PAP therapy. For example, those with high LG at baseline will have the greatest improvement in endothelial dysfunction with PAP therapy compared to other OSA patients with similar disease severity as measured by AHI.

Statistical Analysis Plan: To test change over time after 3 months of PAP therapy in the PLWH+OSA group, we will compare endothelial dysfunction (EndoPAT) at baseline versus 3 months via a paired t-test. Based on Itzhaki and colleagues, we anticipate a mean endothelial function of 1.77 (SD 0.4) in those with untreated OSA, and that a delta of 0.3 represents a clinically important difference based on the effect size of treatment of OSA observed in our prior studies (Ref 127). Assuming a change in mean endothelial function of 0.5 in those with high LG induced OSA vs a change of just 0.2 in those with low LG OSA, we will have adequate power (beta >0.82) to detect this difference between the two groups (alpha = 0.05). As a sensitivity analysis, we will consider multiple regression models adjusting for additional covariates such as age, AHI, medications, mean sleep duration as assessed by actigraphy, and inflammation as assessed by CRP or IL-6 may be included in the modeling if significantly associated with outcome (p<0.10).

References

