9. RESEARCH DESIGN AND METHODS

Under each visit subsection, we have added alternatives for researchers to consider in order to maintain social distancing and perform study activities remotely due to COVID-19. After written informed consent has been obtained, the following procedures will be undertaken:

Daytime Visit 1 (Aim #1)

1. *Anthropomorphic assessment:* Baseline demographics and health status (medical problems, medications, allergies, social history) will be obtained. A basic exam, including height, weight, neck circumference, hip, and waist circumference, blood pressure, and oxygen saturation will be obtained.
2. *Lung Function Assessment using spirometry:* As per American Thoracic Society criteria. In brief, subjects will blow into a pneumotachogram via a mouthpiece with a nose clip in place from full inhalation to complete exhalation.
3. *Questionnaires:* Standard sleep related questionnaires will be used, including the Epworth Sleepiness Scale, Pittsburgh Sleep Quality Index, and Insomnia Severity Index (ISI). In addition subjective assessment of fatigue, depression, quality of life questionnaires, pain, and alcohol consumption will be

used including Functional Assessment of Chronic Illness Therapy Fatigue Scale (FACIT-F), Beck Depression Index-II, SF-36 Item Health Survey (SF-36), Brief Pain Inventory (Short Form), PROMIS pain intensity, PROMIS pain interference, Alcohol Use Disorders Identification Test (AUDIT), and Alcohol Dependence Scale (ADS). Subjects will also be given the FRAM body morphology questionnaire.

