4. *Neurocognitive assessment:* Subjective assessment will be done using, Patient's Assessment of Own Function Inventory (PAOF) questionnaire. Objective assessment of brain function will be done using 10 minute psychomotor vigilance test (PVT). Neurocognitive assessment will be done using NIH Toolbox Cognition. This battery yields three composite scores: overall cognitive function, crystallized cognition and fluid cognition. The two tests of "crystallized cognition" are less sensitive to acquired brain dysfunction and reflect past learning experiences (Oral Reading Recognition and Picture Vocabulary). The five tests of "fluid cognition" assess multiple cognitive domains that are vulnerable to acquired brain dysfunction (i.e., Picture Sequence Memory Task = episodic memory, Dimensional Change Card Sort Task = executive function/flexibility, Pattern Comparison Task = processing speed, Flanker Inhibitory Control and Attention Task = executive function/inhibitory control, and List Sorting Task = working memory).

The NIH Toolbox battery has been nationally normed in a sample of 4,859 participants, English or Spanish speaking, ages 3-85 years, representative of the U.S. population based on gender, race/ethnicity, and socioeconomic status. Based on these data, demographically-corrected T-scores are available to adjust for age, gender, education, language and race/ethnicity.¹¹⁵ Additionally, this assessment tool is the result of an NIH initiative and is used in many studies, which allows for harmonization of findings. It can be completed in approximately 30 minutes.

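### Replacing Bonferroni with Holm's step-down for the secondary outcomes keeps the same 5% family-wise error and never loses a rejection; the gain is small unless many outcomes truly differ

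*SAP*

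**What the plan says.** The SAP's Statistical Considerations set the rules for all aims. On the secondary outcomes they say "All tests of significance for the secondary outcomes will be 2-sided" and "Bonferroni adjustments will be made for multiple comparisons as appropriate". The significance level follows: "A p-value of 0.05 will be considered statistically significant". Results are to be given as point estimates with "interval estimates (95% confidence intervals"; the text does not say whether those intervals are adjusted.

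The only outcome that the SAP calls primary is FACIT-F, in Aim 1. Its sample size paragraph expects that "60 subjects will have OSA and 60 will not".

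Neither document lists or counts the secondary outcomes, or says whether the Bonferroni family is per aim, per domain or study-wide. Protocol section 9 describes many measurements. They include sleep scales ("Epworth Sleepiness Scale, Pittsburgh Sleep Quality Index, and Insomnia Severity Index (ISI"), other questionnaires, the NIH Toolbox composites ("overall cognitive function, crystallized cognition and fluid cognition"), EndoPAT, blood pressure, actigraphy and blood markers. It does not label them secondary outcomes.

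**The concern.** Aim 1 compares symptoms between people living with HIV with and without OSA, so beyond fatigue it poses a question about many outcomes. Single-step Bonferroni tests every one of m outcomes at 0.05/m, however many of the others have already been rejected. Holm relaxes the threshold after each rejection and still holds the family-wise error at 5%. If several outcomes truly differ, the SAP's choice leaves some real differences non-significant that Holm would declare at no extra risk of a false claim. At stake is some power on the secondary comparisons of a fairly small study.

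**Working it through.** **Why Holm cannot do worse.** Order the p-values from smallest to largest. Bonferroni rejects when p ≤ 0.05/m. Holm compares the i-th smallest with 0.05/(m − i + 1) and stops at the first failure.

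- Each Holm threshold is at least 0.05/m. If r p-values lie at or below 0.05/m, they are the r smallest, each passes its Holm step, and all r are rejected.
- Error control: suppose m0 null hypotheses are true and the first of them to be rejected falls at step i. The i − 1 rejections before it are all correct, so i − 1 ≤ m − m0 and m − i + 1 ≥ m0. Its p-value is therefore at most 0.05/m0. The chance that any of m0 true nulls has p ≤ 0.05/m0 is at most m0 × 0.05/m0 = 0.05, whatever the correlation.
- At step 1 Holm's threshold is also 0.05/m, so the chance of at least one rejection is the same under both methods.

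**The plan's own figure.** The SAP gives no power for any secondary outcome. The nearest figure is for FACIT-F ("assuming a mean FACIT-F score of 36 in those without OSA and 30 in those with OSA"), with SD 12 and 60 per group. The effect is 6/12 = 0.5 SD and the expected test statistic is 0.5 × √(60/2) = 2.739. Two-sided at 0.05, power is Φ(2.739 − 1.960) = 0.782 (0.775 by the noncentral t), against about 80% stated. The inputs are usable.

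**Inputs assumed for the secondary outcomes.** m = 20, with m = 10 as a check, because the documents give no count. True effects are 0.5 SD (borrowed from FACIT-F) or 0.25 SD. The number of outcomes that truly differ is varied.

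**Power per true effect under Bonferroni, 0.5 SD.**

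- m = 20: each test at 0.05/20 = 0.0025, critical value 3.023, power Φ(2.739 − 3.023) = 0.388.
- m = 10: each test at 0.05/10 = 0.005, critical value 2.807, power Φ(2.739 − 2.807) = 0.473.

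With no adjustment, 20 independent tests would have a family-wise error of 1 − 0.95^20 = 0.64.

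**Bonferroni against Holm by simulation, m = 20, 60 vs 60, 0.5 SD** (50,000 replicates per row; average power per true effect):

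| Truly different | Correlation | Bonferroni | Holm | Gain, points | Relative gain |
|---|---|---|---|---|---|
| 1 of 20 | 0 | 0.388 | 0.389 | 0.0 | about 0% |
| 5 of 20 | 0 | 0.388 | 0.398 | 1.0 | 1.0/38.8 = 2.6% |
| 5 of 20 | 0.5 | 0.385 | 0.396 | 1.1 | 1.1/38.5 = 2.9% |
| 10 of 20 | 0 | 0.387 | 0.412 | 2.5 | 2.5/38.7 = 6.5% |
| 10 of 20 | 0.5 | 0.387 | 0.415 | 2.9 | 2.9/38.7 = 7.5% |
| 20 of 20 | 0 | 0.388 | 0.461 | 7.3 | 7.3/38.8 = 18.8% |
| 20 of 20 | 0.5 | 0.390 | 0.488 | 9.8 | 9.8/39.0 = 25.1% |

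With correlation 0.3 and 16 of 20 truly different, mean true findings are 5.94 under Bonferroni and 6.83 under Holm: 0.89/5.94 = 15%, or 0.89/16 = 5.6 points per outcome.

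**With m = 10, 0.5 SD.** 1 true: at most +0.1 points. 5 true: +3.0 points (3.0/47.2 = 6.4%). 8 true: 3.70 against 4.25 findings (0.55/3.70 = 15%). All 10 true: +10.3 to +10.6 points.

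**With 0.25 SD.** At m = 20 the gain is at most 0.9 points. With 16 of 20 true, mean findings are 0.72 and 0.76.

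Family-wise error stayed at or below 0.05 within simulation error for both methods. No replicate had a Bonferroni rejection that Holm missed.

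**The case against.** The strongest reply is that this is a preference between two valid procedures. Bonferroni controls the error it is meant to control, and no secondary outcome carries a power claim that could fail. Aim 1's stated hypothesis concerns fatigue and is tested on FACIT-F, outside the sentence in question. All of that stands, and it is why the point is optional.

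A reader might infer from section 9 of the protocol that there are about 20 secondary outcomes. The documents do not support this. They describe measurements, and several have other roles: EndoPAT is the outcome for hypothesis 2B and Aim 3, while actigraphic sleep duration, CRP and IL-6 appear as covariates. Twenty is an assumption; that Holm never rejects fewer does not depend on it.

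A reader might also take 15% as the expected gain. That figure needs 16 of 20 outcomes to differ by as much as the primary outcome is assumed to. Even then Holm misses 16 − 6.83 = 9.17 true differences, against 16 − 5.94 = 10.06 for Bonferroni. Most of the lost power is the price of family-wise control itself: from 0.782 unadjusted to 0.388 at m = 20.

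The last reply is that Bonferroni has simple simultaneous intervals, which suits a plan that leads with interval estimates. This is a fair reason for Bonferroni. Its weight is limited because the SAP mentions only 95% intervals and no adjusted ones. It would be wrong, however, to read the SAP as having planned unadjusted intervals; it is silent.

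**Conclusion.** The point holds as an efficiency improvement. Holm gives the same 5% family-wise guarantee, needs no further assumption, and never rejects fewer hypotheses than the method named in the SAP. The direction of the gain is certain; its size cannot be computed from the documents. Under the assumed 20 outcomes, 60 vs 60 and 0.5 SD, it is about 0%, 3%, 7% and 15% more true findings with 1, 5, 10 and 16 true differences. With 10 outcomes it is about 6% with 5 true and 15% with 8 true. At 0.25 SD it is negligible in absolute terms. The chance of finding at least one difference is unchanged.

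A reader might infer that the SAP contains an error, or that real differences in the main Aim 1 comparison would be missed. Neither follows: Bonferroni is valid, the sentence covers secondary outcomes only, and no primary result, sample size or error guarantee changes.

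**What to change.** In Statistical Considerations, replace Bonferroni with Holm step-down at family-wise 0.05. Apply it to whatever family of secondary outcomes the SAP intends for Bonferroni. Do not narrow that family to one per aim as part of the change: if the intended family is study-wide, Holm at 0.05 within each aim would not hold the same error. The sponsor has to state which outcomes form the family, because neither method can be applied as pre-specified without that. Add a sentence saying that the 95% confidence intervals are not adjusted for multiplicity.

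The cost is a short text change made before outcome data are analysed. R, which the SAP already names, offers Holm as a standard option in p.adjust. No extra participants, data or assumptions are needed. The one real downside is that Holm has no simple matching simultaneous confidence intervals, so an outcome's interval and its adjusted test may disagree. If the sponsor wants simultaneous intervals, that is a sound reason to keep Bonferroni and say so.
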